6.3.2 Handling of dropouts and missing data

Patients not completing the clinical procedure as intended by the investigator are considered as drop-outs as the evaluation form will lack information of the device. Drop-outs are

Protocol – Non-interventional study

11/13

Project/Product Name: AuraOnce performance observation
Study ID: CIS-016

07-OCT-2019

compensated in the sample size estimation to ensure that a complete data set is collected for minimum 15 patients. Missing data will not be imputed.

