3. OBJECTIVES AND HYPOTHESES

The objective of this study is to observe the performance of the AuraOnce through clinical assessment and endoscopic imaging to ensure ongoing documentation on quality of the product in regards to correct placement remains high.

This is an observational study with no hypothesis. However, a success criterion is set saying that in 90% of the cases the AuraOnce must be correctly centred above vocal cords with no clinical significant air leak and using maximum three placement attempts.

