4.3.3 Subject withdrawal or discontinuation

Patients not completing the clinical procedure as intended by the investigator are considered as drop-outs as the evaluation form will lack information of the device. In case of drop-outs the study will not be completed until the minimum number of subjects is included.

Subjects will be withdrawn from the clinical investigation for the following reason:

- a. Withdrawal by investigator for e.g. safety reasons

The reason for withdrawal will be investigated and carefully documented in the appropriate section of the case report form (CRF).

If a subject is replaced the new subject is given a new subject number.

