4.3.5 Duration of the clinical investigation

The data collection is expected to last three days within a two months period. The subjects are included in the study when the investigator has ensured that they fulfill the in- and exclusion criteria and they are completed when the bronchoscopist have confirmed the laryngeal mask placement (by taking a picture) and starts the planned bronchoscopy procedure. The expected duration of each subject's participation is estimated to be less than one hour.

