6.2 Pass/fail criteria

In 90% of the cases the AuraOnce must be correctly centred above vocal cords with no clinical significant air leak and using maximum 3 placement attempts.

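### The drop-out rule allows a placement abandoned before the confirming picture to be replaced and left out of the 90% pass/fail criterion, because the criterion's denominator is not defined

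*Combined protocol and SAP*

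**What the plan says.** Section 6.2, headed as pass/fail criteria, sets the study's only decision rule: "In 90% of the cases the AuraOnce must be correctly centred above vocal cords with no clinical significant air leak", with at most three placement attempts. Section 3 gives the same rule: "a success criterion is set saying that in 90% of the cases the AuraOnce must be correctly centred above vocal cords". Neither section says whether a case is an enrolled subject, an attempted insertion or a subject with complete data.

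Sections 4.3.3 and 6.3.2 define drop-outs in the same words: "Patients not completing the clinical procedure as intended by the investigator are considered as drop-outs". Both explain that the evaluation form will then lack device information. Drop-outs are said to be "compensated in the sample size estimation to ensure that a complete data set is collected for minimum 15 patients", and "Missing data will not be imputed". Section 4.3.3 adds "In case of drop-outs the study will not be completed until the minimum number of subjects is included" and "If a subject is replaced the new subject is given a new subject number".

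Section 4.3.5 fixes the point of completion: "they are completed when the bronchoscopist have confirmed the laryngeal mask placement (by taking a picture"), and the planned bronchoscopy starts. Under section 4.4.6 the number of attempts and leakage (yes/no, with signs) go on the CRF after insertion. That is before the picture described in section 4.4.7.

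**The concern.** The study judges whether the mask can be seated and sealed within three attempts. A mask that cannot be seated or sealed is a plausible reason for not completing as intended, so the drop-out event can be the outcome itself. The rule nevertheless puts such a case in the same class as a cancellation that has nothing to do with the device.

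Two analysts with the same forms could then reach opposite verdicts. One would take the 90% over complete data sets, the other over all attempted insertions. The first reading can only raise the success rate, because every abandoned failure leaves the denominator and a new subject takes its place.

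There is a second, smaller problem. In sections 4.3.3 and 6.3.2 the procedure to be completed could mean the bronchoscopy, whereas sections 4.3.5 and 4.4.7 end the study part before the planned bronchoscopy proper. On that reading, a subject with a full device assessment could also be dropped.

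**Working it through.** **Inputs.** The 90% threshold is from section 6.2. The range of 15 to 20 enrolled subjects is from sections 4.3 and 6.1. The aim of 15 complete data sets is from section 6.3.2. There is no sample-size figure to reproduce: section 6.1 says no calculation was made, although section 6.3.2 says drop-outs are compensated in one. The documents give no success, drop-out or abandonment rate.

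**Step 1: successes needed.** The smallest whole number at or above 0.9n is:

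| n | 15 | 16 | 17 | 18 | 19 | 20 |
|---|---|---|---|---|---|---|
| successes needed | 14 | 15 | 16 | 17 | 18 | 18 |
| failures allowed | 1 | 1 | 1 | 1 | 1 | 2 |

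**Step 2: does the denominator change the verdict?** Let n be complete cases, r recorded failures and k abandoned placements, with n + k at most 20. Compare (n − r)/n with (n − r)/(n + k). No assumed rate is needed.

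| Complete cases | r = 1: completers | r = 1, k = 1: all attempted | r = 0, k = 2: all attempted |
|---|---|---|---|
| 15 | 14/15 = 93.3% pass | 14/16 = 87.5% fail | 15/17 = 88.2% fail |
| 16 | 15/16 = 93.8% pass | 15/17 = 88.2% fail | 16/18 = 88.9% fail |
| 17 | 16/17 = 94.1% pass | 16/18 = 88.9% fail | 17/19 = 89.5% fail |
| 18 | 17/18 = 94.4% pass | 17/19 = 89.5% fail | 18/20 = 90.0% pass |
| 19 | 18/19 = 94.7% pass | 18/20 = 90.0% pass | exceeds the cap |

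With r = 0 the completers' rate is 100%. A single abandonment then does not reverse the verdict (for example 15/16 = 93.8%).

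**Step 3: illustration with assumed rates.** Let p be the true success rate and a the share of failures that are abandoned. Enrolment stops at 15 complete, with a cap of 20.

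- Completers only: the success rate among completers is q = p / (1 − (1 − p)a). The chance of passing is q^15 + 15 q^14 (1 − q), times the chance of reaching 15 complete by the cap. That last chance is above 99.9% for every row below.
- All attempted: a pass needs no abandonment and at most one failure, or one abandonment and no other failure. The chance is p^15 + 15 p^14 (1 − p)(1 − a) + 15 p^15 (1 − p)a.

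Check at a = 0 and p = 0.95: both give 0.95^15 + 15 × 0.95^14 × 0.05 = 82.9%. Example at p = 0.90 and a = 0.50: q = 0.90/0.95 = 0.947, which gives 81.4%. All attempted gives 0.2059 + 0.1716 + 0.1544 = 53.2%.

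| p | Failures abandoned | Completers only | All attempted | Gap (points) |
|---|---|---|---|---|
| 95% | 5% | 84.2% | 82.8% | 1.4 |
| 95% | 10% | 85.4% | 82.7% | 2.7 |
| 95% | 25% | 89.1% | 82.4% | 6.6 |
| 95% | 50% | 94.5% | 82.0% | 12.5 |
| 90% | 5% | 57.3% | 54.7% | 2.6 |
| 90% | 10% | 59.8% | 54.6% | 5.3 |
| 90% | 25% | 67.7% | 54.0% | 13.7 |
| 90% | 50% | 81.4% | 53.2% | 28.3 |

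Gaps are taken from unrounded values.

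**The case against.** The study is descriptive and uncontrolled, states no hypothesis and serves quality control. A CRF is required for every enrolled subject (section 4.4), and withdrawal reasons are documented (section 4.3.3). One observer attends all data collection (section 4.5.5). The cap of 20 limits replacements to five if 15 are to be complete. An excluded case would therefore be traceable. All of this stands and lowers the severity, but none of it links a drop-out to the 90% criterion, and no sensitivity count is planned.

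The stated reason for drop-out status, missing device information, also suggests a narrower reading. A form that already shows more than three attempts does not lack the information that decides the case, so it need not be a drop-out. That is a fair reading, but the text does not settle it, and it does not cover a placement abandoned with no deciding field yet filled in.

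A reader might infer that any leak noted on the form is already a failure. The documents do not support this. Section 6.2 fails a case only for a clinically significant leak, while section 4.4.6 records leakage as yes or no with its signs. Treating every recorded leak as a failure would change the endpoint, not clarify the denominator.

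**Conclusion.** The concern holds as a gap that permits exclusion. A reader might go further and infer that the plan requires failed placements to be removed, or that its result is bound to be biased. Neither follows: no section expressly takes drop-outs out of the 90%, and none says they count as failures. If no placement is abandoned, the rule causes no bias.

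The firm evidence is the reversal arithmetic, which needs no assumed rate. One abandonment decides the verdict at 15 to 18 complete cases if one failure is recorded, and two decide it at 15 to 17 if none is. The pass probabilities are illustrations only. When 5 to 50% of failures are abandoned, the gap runs from 1.4 to 12.5 points at 95% true success and from 2.6 to 28.3 points at 90%. The upper ends need half of all failures to be abandoned, and nothing in the documents says that is likely.

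Severity: should be fixed. The effect is conditional and the study is descriptive, but this is its only pass/fail rule.

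**What to change.** In sections 6.2 and 6.3.2, with section 4.3.3 aligned:

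1. Define the pass/fail denominator as all enrolled subjects in whom AuraOnce insertion was attempted.
2. Count non-completion for a placement- or device-related reason as a failure.
3. Let a recorded failed component, as section 6.2 defines it, decide the case even if other fields are missing. These components are a clinically significant air leak with the judgement documented, a mask not correctly centred, or more than three attempts. A bare yes for leakage is not by itself a failure.
4. Keep in the denominator subjects whose device assessment was complete before the bronchoscopy was abandoned, and align the term for the procedure with the study end point in sections 4.3.5 and 4.4.7.
5. Exclude and replace only subjects with no attempted insertion, or those stopped for a documented unrelated reason with no failed component recorded. List all drop-outs by reason.

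Items 1 and 2 are the essential change. The others keep it from being applied unevenly.

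The cost is protocol wording and no extra patients. Attempts, leakage and the withdrawal reason are already collected. The CRF must also class the reason as placement- or device-related or not, and record the judgement on whether a leak was clinically significant. The downside for the sponsor is that the reported success rate may be lower and a pass may become a fail.

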7. DATA MANAGEMENT

A database will be set up, and two individuals at Ambu A/S will perform double data entry. Any unclear data points will be highlighted in a data clarification form that will be sent to the responsible investigator for clarification. An error list will be generated, and errors corrected by Ambu A/S staff.

7.1 Data review and cleaning

The CRF must be filled in for each subject that is included in the investigation.

The CRF is in English and should be filled in English when possible.

Missing data not recorded on the day of the procedure should be filled in later accompanied by date and signature. Data that are evaluated as incorrect by investigator should be crossed over with ink allowing the "old data" to be seen (example). The investigator shall then write the corrected data, signed and dated.

The principal investigator at the clinical site will perform primary data collection by entering the data into the CRF. Only the principal investigator or other pre-designated clinical investigation site personnel will be authorized to enter data.

The sponsor's designated monitor shall ensure appropriate training on data entry is provided prior to the start of the clinical investigation to all site personnel involved.

The principal investigator can delegate tasks to his/her collaborators, however the roles and responsibilities as time period of involvement for each clinical site personnel must be documented on the site personnel log as well as training received before getting involved with the clinical investigation.

Clinical site personnel not trained and not officially identified by his/her name and signature cannot enter data in the CRFs.

The principal investigator shall approve and date each CRF.

The monitor shall verify all critical data points and issue queries for the authorized clinical site personnel to answer.

A CRF section shall be considered complete when all data are completed, verified by the monitor, outstanding queries resolved and signed off by the principal investigator.

A critical quality control will be performed continuously by the designated observer at the site.

7.2 Data retention

The sponsor and principal investigator shall maintain the clinical investigation documents as required by the applicable regulatory requirements. For non-implants the investigator binder, including CIP, CIR and copies of CRF's, , must be kept on site for at least 5 years after the clinical investigation report has been signed.

The sponsor will file original CRFs for rest of the products' lifetime + 10 years. Moreover, adverse event forms, statistical analysis, agreements, approvals, investigators' CVs, CIP, and CIR will also be filed.

Protocol – Non-interventional study

12/13

Project/Product Name: AuraOnce performance observation
Study ID: CIS-016

07-OCT-2019

8. DEVICE ACCOUNTABILITY

The site included in the study will make their daily used bronchoscopes available for the procedure.

The site will free of charge receive 20 Ambu® AuraOnce devices in each of the sizes used for adults (size 3, 4, 5 and 6). Any devices remaining after the end of the study will be accounted for and shall be returned to Ambu®.

There are no requirements regarding device accountability for CE marked devices. However, for logistical reasons the Sponsor will account for all devices delivered to and returned from the Investigators in a Device Accountability Form kept at Sponsor's address.

9. STATEMENTS OF COMPLIANCE

The clinical investigation will be conducted according to the guidelines established in the Declaration of Helsinki (4). Good clinical practice

The clinical investigation processes will comply with good clinical practice as outlined in ISO 14155 (2).

9.1 Regulatory compliance

The clinical investigation processes shall be performed in compliance with all applicable regulatory requirements in addition to the above defined requirements for good clinical practices. Where regulatory requirements are less or more stringent than the requirements outlined in ISO 14155 (2) the most stringent requirements will need to be complied with.

This includes the Council Directive 93/42 EEC of 14 June 1993 and amendment 2007/47/EC (1).

9.2 Patient information

Not applicable for this study.

9.3 Informed consent

Not applicable for this study.

